9.4.2 PK and ADA_b analyses

Plasma bimekizumab concentrations will be summarized for the PK-PPS at each time point using descriptive statistics. In addition, PK model-based analyses may be performed and reported separately.

Antidrug antibody data will be evaluated for each study participant in the SS, and rates of ADA_b-positive study participants will be calculated. Neutralizing ADA_b data will also be evaluated. Further details will be provided in the SAP.

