After completion of the Week 16 assessments, which are the last assessments in the 16-week Initial Treatment Period, study participants will enter the 16-week Maintenance Treatment Period. The first dose of IMP will be administered at Week 16 after all assessments are performed. During the Maintenance Treatment Period, study participants will return to the clinic Q4W up to Week 32 to maintain the study blind.

The treatment during the Maintenance Treatment Period (Week 16 to Week 32) will be based on the following rules:

- Study participants in the bimekizumab 320mg Q4W arm will receive bimekizumab 320mg every 8 weeks (Q8W). These study participants will also receive placebo injections at visits between dosing with bimekizumab to maintain blinding procedures.
- Study participants in the placebo arm will receive bimekizumab 320mg Q4W.

[figure not shown]
- SFU Period

After completion of the 16-week Maintenance Treatment Period, study participants will enter the SFU Period after the final dose of IMP.

Study participants withdrawing early from the study will undergo the PEOT Visit assessments and will enter the SFU Period.

All study participants, including those withdrawn from IMP, will have a SFU Visit 17 weeks after the last dose of IMP.

Figure 1-1: Study schematic

IGA 0/1=Investigator's Global Assessment response clear (0) or almost clear (1) with ≥ 2 -category improvement relative to Baseline; PASI90=90% or greater improvement from Baseline in the Psoriasis Area and Severity Index score; Q4W=every 4 weeks; Q8W=every 8 weeks; w=week

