3 POPULATIONS FOR ANALYSIS

The Enrolled Set (ES) will consist of all study participants who have given informed consent.

The Randomized Set (RS) will consist of all randomized study participants.

The Safety Set (SS) will consist of all study participants who receive ≥ 1 dose of IMP (bimekizumab or placebo).

The Full Analysis Set (FAS) will consist of all randomized study participants who receive ≥ 1 dose of IMP and have a valid measurement for each of the co-primary efficacy endpoints at Baseline.

The Active Medication Set (AMS) will consist of all study participants who receive ≥ 1 dose of active IMP (bimekizumab).

The Maintenance Set (MS) will consist of all study participants who receive ≥ 1 dose of active IMP (bimekizumab) in the Maintenance Treatment Period.

The Per-Protocol Set (PPS) will consist of all study participants in the RS who have no important protocol deviations affecting the co-primary efficacy endpoints. Important protocol deviations

will be predefined, and study participants with important protocol deviations will be evaluated during ongoing data cleaning meetings prior to database lock. The classification of PPS will be determined at blinded data evaluation meeting before unblinding of the data. The classification of study participants with important protocol deviations related to treatment group information will be re-determined after general unblinding.

The Pharmacokinetics Per-Protocol Set (PK-PPS) will consist of all randomized study participants who receive ≥ 1 dose of active IMP (bimekizumab) and provide ≥ 1 quantifiable plasma concentration post dose without important protocol deviations that would affect the concentration.

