If a study participant has only negative ADA_b samples or only 1 missing/inconclusive sample with all negative ADA_b samples up to that time point, the study participant will be classified as negative. An exception remains for the Baseline Visit where only 1 sample could be available. If the sample is missing/inconclusive, then the sample will be classified as being negative for the cumulative ADA_b status.

Otherwise, the study participant will be classified in the missing ADA_b category.

4.6.1.4.1.3 Overall ADA_b status (Positive, Negative, Missing)

A participant's Overall ADA_b Status will be derived for the following periods:

- Overall ADA_b Status in the Initial and Maintenance Treatment Period (combined): Including any visit during the Initial and Maintenance Treatment Period (as defined in Section 4.1.1.2). Thus, this summary will exclude data obtained at the SFU visit and will include data obtained at Baseline. This summary will display the overall ADA_b status up to Weeks 16 and 32 by treatment group (Placebo/BKZ 320mg Q4W, BKZ 320mg Q4W/Q8W).

For each time period, the participant will be classified as:

- Positive if the study participant has at least one positive sample up to the time point of interest (regardless of having missing/inconclusive data).
- Negative if the study participant has all the samples negative or only one missing/inconclusive sample with negative ADA_b samples up to the timepoint of interest.
- Missing if the study participant has missed more than one ADA_b result (or have more than one inconclusive sample) and all other available ADA_b samples are negative up to the time point of interest.

4.6.1.4.1.4 ADA_b categories

In addition, the ADA_b status will be further classified according to the following ADA_b categories:

- **Pre ADA_b negative – treatment emergent ADA_b negative (Category 1):** Includes study participants who are negative at Baseline and antibody negative at all sampling points (including SFU); one post-Baseline missing/inconclusive sample is allowed for study participants with pre-ADA_b negative sample. This group also includes study participants

who have a missing/inconclusive pre-treatment sample (eg, either missing/inconclusive or insufficient volume) at Baseline with all post-Baseline samples as ADA_b negative.

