4.6.1.4.2 Immunogenicity analyses

4.6.1.4.2.1 ADAb and NAb summaries

All analyses will be prepared on the AMS by treatment group, unless specified otherwise.

The following summaries of ADAb data will be prepared by treatment group:

- Summary table displaying the number and percentage of study participants with ADAb sample status (positive, negative, total of positive and negative, missing) at each visit, and overall ADAb status during the respective treatment periods of interest (overall up to Week 16 and Week 32 and separately overall up to Week 16 and Week 32 for the efficacy subgroup analysis). If $\geq 95\%$ of study participants are in the nonmissing groups, the missing group will not be displayed.
- Number and percentage of study participants with first occurrence of ADAb-positive result by visit by ADAb category:
 - Any ADAb-positive: ADAb-positive sample regardless of category during the treatment period
 - Category 7: Total treatment-emergent ADAb positive (combination of categories 2 and 5 [PreADAb negative – treatment-emergent ADAb-positive; and PreADAb-positive – treatment emergent ADAb boosted positive, respectively])

Study participants who are either treatment-emergent ADAAb positive or treatment-boosted ADAAb-positive for the first time at the specified time point in the study and the cumulative number and percentage of study participants with any ADAAb-positive sample and treatment-emergent ADAAb-positive and treatment boosted ADAAb-positive results at each time point will be summarized.

- Number and percentage of study participants in each of the 9 ADAAb categories (as defined in Section 4.6.1.4.1.4) up to Week 32 (repeated including SFU in the final analysis).
- All individual study participant-level ADAAb results will be listed including the screening assay, confirmatory assay, ADAAb sample status, and titers if applicable. Note that titer results will only be available if the confirmatory assay is positive. The listing will also include flags and reasons for exclusion for ADAAb measurements that are excluded from the by-visit summaries, as well as information on whether the bimekizumab concentration exceeded the ADAAb assay drug tolerance limit.

The following summaries of NAb data will be prepared by treatment group:

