4.8 Changes to protocol-planned analyses

For key secondary efficacy endpoints, it's stated in protocol section 9.3.2.1 that missing data for these variables will also be imputed using multiple imputation (MI) similar to the sensitivity analyses for the co-primary endpoints. In addition, analyses will be repeated using the FAS and the NRI method. However, in SAP section 4.3.1.3 no sensitivity analyses based on MI or based on FAS with NRI method are provided.

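### Antidrug-antibody summaries move from the Safety Set to the Active Medication Set without being recorded as a change, and up to Week 16 this can remove participants from the placebo column only

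*SAP*

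**What the plan says.** Protocol 9.4.2 states: "Antidrug antibody data will be evaluated for each study participant in the SS". It adds that neutralizing-antibody (NAb) data will also be evaluated, without naming a set, and leaves further detail to the SAP.

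SAP 4.6.1.4.2.1 opens the ADAb and NAb summaries with: "All analyses will be prepared on the AMS by treatment group, unless specified otherwise". The immunogenicity section names no exception on the Safety Set.

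Under SAP Section 3, one dose of bimekizumab or placebo puts a participant in the Safety Set, and the AMS needs one dose of bimekizumab. The placebo arm first becomes eligible for the AMS in the Maintenance Treatment Period, from Week 16: "Study participants in the placebo arm will receive bimekizumab 320mg Q4W" (SAP 1.2).

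Overall ADAb status is reported as "status up to Weeks 16 and 32 by treatment group" (SAP 4.6.1.4.1.3), with columns Placebo/BKZ 320mg Q4W and BKZ 320mg Q4W/Q8W and with Baseline data included. NAb categories are also summarized up to Week 16.

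SAP 4.8 records one departure from the protocol, for the key secondary endpoints: "no sensitivity analyses based on MI or based on FAS with NRI method are provided". It does not mention the ADAb analysis set.

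**The concern.** The protocol names one population and the SAP uses another, with no entry where changes are meant to be listed. The two sets differ in one arm only. A bimekizumab participant joins the AMS at the first injection. A placebo participant joins only on receiving the switch dose, which is an event after randomization. A placebo column up to Week 16 built on the AMS is therefore not the treated placebo group, although the bimekizumab column beside it is the treated bimekizumab group.

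At stake is a descriptive reference. Participants on placebo are the only ones sampled after Baseline without drug exposure, so their Week 8 and Week 16 results show what the assay returns as background or false positives over the same weeks. The observed bimekizumab ADAb rate is naturally read against that.

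**Working it through.** Neither document gives an expected ADAb rate or a dropout figure, so there is no plan figure to reproduce. The check is a comparison of texts, followed by an illustration of size.

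**Who is removed**

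1. ADAb samples through Week 16 are scheduled at Baseline, Week 8 and Week 16 (Protocol Table 1-1).
2. SAP 4.1.1.2 allows a participant to finish the Week 16 assessments and never start maintenance. Such a placebo participant counts as completing the Initial Treatment Period and can have all three samples, yet is outside the AMS.
3. A placebo participant who leaves earlier can also contribute. Protocol 8.8 asks for a sample at the final visit of those who discontinue. SAP 4.1.3 makes a special rule that sends early-termination ADAb samples to the next ADAb visit. Someone who leaves before Week 8 with such a sample has Baseline and Week 8 results and one missing result. SAP 4.6.1.4.1.3 can still classify that participant as negative or positive.
4. The AMS rule removes all of these from the summaries.

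**What the SAP does elsewhere**

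The by-visit laboratory tables (4.5.3.1), by-visit vital-sign tables (4.5.3.2) and IGRA table (4.5.3.4.2) use the same pair of sequence columns on the Safety Set. SAP 4.1.4 puts initial-period safety, with its placebo column, on the Safety Set. It pairs the AMS with bimekizumab columns that take only post-switch data from the placebo arm. The ADAb tables combine an AMS population with a placebo column and pre-switch data.

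**Size, with assumed counts**

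Inputs: 120 participants randomized 3:1 (Protocol 4.1, SAP 1.2), so 120 × 3/4 = 90 bimekizumab and 120 × 1/4 = 30 placebo. Protocol 9.3.1 expects few discontinuations before Week 16 but gives no number. Assumptions: all 30 placebo participants are dosed, 2 are ADAb-positive by Week 16, and L leave before an active dose.

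Safety Set rate = 2/30 = 6.7%.

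The AMS rate lies between max(0, 2 − L)/(30 − L) and 2/(30 − L).

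| L | Placebo n in AMS | Lowest rate | Highest rate | Bimekizumab n |
|---|---|---|---|---|
| 0 | 30 | 2/30 = 6.7% | 2/30 = 6.7% | 90 |
| 1 | 29 | 1/29 = 3.4% | 2/29 = 6.9% | 90 |
| 3 | 27 | 0/27 = 0% | 2/27 = 7.4% | 90 |
| 5 | 25 | 0/25 = 0% | 2/25 = 8.0% | 90 |

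The 0% entries are unlikely extremes. If leaving is unrelated to ADAb status, the chance that both positives are among the leavers is C(3,2)/C(30,2) = 3/435 = 0.7% for L = 3, and C(5,2)/C(30,2) = 10/435 = 2.3% for L = 5. Under the same condition the expected number of positive leavers is 2L/30. The expected AMS rate is then (2 − 2L/30)/(30 − L) = 2/30, the Safety Set rate.

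**The case against.** The strongest reply is that little depends on this. ADAb is a tertiary endpoint, the tables are descriptive, no test between arms is planned, and early dropout is expected to be low. All of that stands and limits the weight of the point.

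Four stronger readings are tempting, and the documents do not support them.

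- *The placebo rate is biased.* Nothing in the documents suggests that leaving placebo is related to ADAb status in people who have not received the drug. If it is unrelated, the expected rate is unchanged and only some precision is lost.
- *The placebo column is the only measure of background reactivity.* Pre-existing reactivity is also measured at Baseline in the bimekizumab arm and summarized in the ADAb categories. Only the post-Baseline, drug-free samples are unique to placebo.
- *The protocol requires the Safety Set for NAb.* It names that set only in the ADAb sentence.
- *The data are lost.* The rule governs the immunogenicity outputs. SAP 4.1 promises complete listings of documented data, although the participant-level ADAb listing itself falls under the AMS sentence, so its coverage is unclear.

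It can also be said that Protocol 9.4.1 assigns the AMS to safety summaries covering the initial and/or maintenance period, and that one population suits sequence columns followed to Week 32. That supports the AMS for the later summaries. It does not displace Protocol 9.4.2, which is the specific provision for ADAb. Leaving further details to the SAP permits elaboration, but a replacement of the named set should be listed as a change.

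**Conclusion.** The SAP contradicts the protocol on the ADAb analysis set and does not record the change. Whenever a dosed placebo participant leaves before the switch dose, the placebo denominator up to Week 16 shrinks while the bimekizumab denominator does not. The size is probably small: with 1, 3 or 5 leavers out of 30 (assumed), the placebo n is 29, 27 or 25. If nobody leaves, the two sets coincide and nothing changes. ADAb rates after active exposure are unaffected. The conclusion assumes that the placebo arm receives no bimekizumab before Week 16. A placebo participant given it in error would be in the AMS, and SAP 4.1.4 reallocates such cases for safety analyses. This is a minor point, but it is worth correcting before the tables are produced.

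**What to change.** In SAP 4.6.1.4.2.1, prepare the following on the Safety Set:

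- ADAb sample status by visit through Week 16;
- overall ADAb status up to Week 16;
- first-occurrence and cumulative ADAb results through Week 16.

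Treat the NAb summary up to Week 16 the same way for consistency, although the protocol names no set for it.

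Keep the AMS for summaries up to Week 32, for those including the Safety Follow-Up visit, and for the ADAb categories. Record that AMS use in SAP 4.8 as a change from Protocol 9.4.2.

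The SAP currently puts by-visit status and overall status up to Weeks 16 and 32 in one summary table. Either split off the part through Week 16 or show the denominator on each row.

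The cost is a short SAP edit and a population flag in the programs. The one downside is that the placebo denominator may differ between the Week 16 and Week 32 summaries, which a footnote can explain.

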4.1.2 Definition of baseline values

A Baseline value for a study participant is defined as the latest measurement for that study participant up to and including the day of first IMP administration, unless otherwise stated. If a Baseline assessment is taken on the same day as first IMP administration, it is eligible to be used as the Baseline value, even in the case that the time of the assessment is recorded as taking place after the time of first IMP administration. This is considered acceptable as this measurement is still the best representation of the Baseline value of the given assessment since it is highly unlikely that the IMP could have an impact on any measurement in such a short period of time. However, such cases should be rare as study center personnel are instructed to do all assessments at the Baseline visit prior to administering IMP. One exception to this rule is plasma concentration. If Baseline plasma concentration is measured at a time after the first IMP administration, then it should not be eligible to be considered as a Baseline plasma concentration. Such cases should be discussed with the quantitative clinical pharmacologist. If a Baseline measurement is missing or not collected, and a Screening value is available, the Screening value will be utilized as Baseline instead.

Baseline values for component scores should be computed using components from the same visit where the relevant measurements were recorded prior to dosing. For example, if the component scores on the Baseline visit cannot be derived due to missing components, the Baseline value for the component score should be calculated using the Screening visit values if the Screening visit has all of the components.

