4.5.2.1 Data considerations

TEAEs are defined as those AEs that have a start date on or following the first dose of IMP through the final dose of IMP + 119 days (covering the 17-week SFU period). If it is not possible (due to partial dates) to determine whether or not an AE is treatment-emergent then it will be assumed to be a TEAE.

The rules for imputing partial AE start or stop dates are described in Section 6.8.1.2.

If the intensity of an AE is unknown, it is considered as severe. If the relationship to study drug is missing, it is considered as related.

AEs will be presented as “number of study participants (percentage of study participants) [number of events]”. In this style of output, “[number of events]” will include all cases of an AE including repeat occurrences in individual study participants, while “number of study participants” will count each study participant only once.

AE summaries by System Organ Class (SOC), High Level Term (HLT) and Preferred Term (PT) will be ordered alphabetically for SOC and HLT within SOC and in terms of decreasing frequency for PT within HLT in the bimekizumab treatment group, and in the event of ties, PT will be sorted alphabetically.

AE summaries by PT will be ordered in terms of decreasing frequency for PT within the bimekizumab treatment group, and in the event of ties, PT will be sorted alphabetically.

Study participant time at risk represents the time a study participant is at risk for having an AE. The definitions for study participant time at risk (in days) are outlined in Section 4.5.1. These definitions will be used for exposure-adjusted AE summaries.

Selected AE summaries will include the exposure-adjusted incidence rate (EAIR) with associated 95% CI and the exposure-adjusted event rate (EAER).

The EAIR is defined as the number of study participants (n) with a specific AE adjusted for the exposure and will be scaled to 100 patient-years:

$$EAIR = 100 \times n / \sum_{i=1}^N (T_{Exp(i)})$$

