- **Pre ADA_b negative – treatment emergent ADA_b positive (Category 2):** Includes study participants who are ADA_b negative at Baseline and ADA_b positive at any sampling point post treatment (including SFU). This group also includes study participants who have a missing pre-treatment sample (either missing or insufficient volume) at Baseline with one or more ADA_b positive post-treatment samples.
- **Pre ADA_b positive – treatment emergent reduced ADA_b (Category 3):** Includes study participants who are ADA_b positive at Baseline, and ADA_b negative at all sampling points post treatment (including SFU).
- **Pre ADA_b positive – treatment emergent unaffected ADA_b positive (Category 4):** Includes study participants who are positive at Baseline and are positive at any sampling point post treatment (including SFU) and all post-Baseline samples have titer values <2.07 times the Baseline titer (where 2.07 is Minimum Significant Ratio [MSR]).
- **Pre ADA_b positive – treatment boosted ADA_b positive (Category 5):** Includes study participants who are positive at Baseline and have at least one post-treatment sample (including SFU) that has titer value ≥ 2.07 times the Baseline titer (where 2.07 is MSR).

Note: For any study participant who is positive at Baseline and positive at a post-Baseline time point, but for whom titers are not available to determine treatment unaffected or treatment boosted status, the study participant will be considered as treatment boosted (ie, Category 5), assuming no other samples are available.
- **Inconclusive (Category 6):** Includes study participants who have a positive pre-treatment sample and some post-treatment samples are missing/inconclusive, while other post-treatment samples are ADA_b negative.
- **Total treatment-emergent (Category 7 [Categories 2 and 5 combined]):** Includes study participants who are pre ADA_b negative – treatment emergent ADA_b positive (Category 2) and pre ADA_b positive – treatment boosted ADA_b positive (Category 5).
- **Total prevalence of pre-ADA_b positivity (Category 8 [Categories 3, 4, 5, and 6 combined]):** Study participants that are tested ADA_b positive at Baseline.

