- **Missing (Category 9):** Includes study participants who have a negative or missing/inconclusive pre-treatment sample at Baseline and more than one post-treatment samples that are missing/inconclusive, while other samples are ADA_b negative. Also includes study participants who have a missing/inconclusive pre-treatment sample at Baseline, and only one missing post-Baseline sample with no ADA_b-positive.

4.6.1.4.1.5 ADA_b status groups for efficacy endpoint summaries

For the efficacy endpoint by ADA_b summaries (described below), the following ADA_b-efficacy status groups are defined:

- **ADA_b-positive** - Defined as study participants having at least 2 ADA_b-positive samples up to the time point of interest (ie, excluding Baseline, excluding SFU) regardless of other ADA_b-negative samples and/or missing or inconclusive samples

- ADAb-negative - Defined as study participants for whom either
 1. all samples to the time point of interest are ADAb-negative and there are no missing or inconclusive samples,
 2. only one sample is ADAb-positive and all other to the time point of interest (including Baseline) are ADAb-negative or missing/inconclusive, or
 3. only one sample is missing/inconclusive and the remaining ADAb samples are negative.
- Missing - Defined as study participants who do not fulfil the criteria for one of the 2 groups listed above.

The ADAb data from Baseline up to the time point of interest will be used to derive the ADAb-efficacy status groups.

The rationale for requiring at least 2 time points in which the participant is confirmed positive is to exclude individuals who have only one occurrence of ADAb levels during the period of interest. Including such study participants would increase the number of ADAb-positive participants with potentially no impact on efficacy.

4.6.1.4.1.6 Neutralizing anti-bimekizumab antibodies (NAb) categories

The NAb will be assessed using IL-17AA- and IL-17FF- specific assay methods, respectively. A NAb result will be positive or negative to each specific NAb assay or both.

Any NAb results derived from samples with drug concentrations higher than the drug tolerance limits of the NAb assays (100µg/mL) will be labeled 'inconclusive'. All inconclusive results will be regarded as missing.

Study participants will be assigned an overall NAb classification, inclusive of Baseline and post-Baseline results from NAb assay:

- NAb negative:

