- Number and percentage of PASI90 responders at Week 16 and Week 32 as a function of Week 16 and Week 32 ADAb titer categories (categorized as ≤ 100 [at or below the MRD of the assay], $>100 - < \text{median}$ [of non-missing titer values >100], and $\geq \text{median}$ [of non-missing titer values >100]). This will be repeated for IGA 0/1 responders at Week 16 and at Week 32. These data will also be presented graphically (for the figure, any study participant with ADAb-positive/ADAb titer missing is included ≤ 100 group).
- Individual plots of bimekizumab concentrations, ADAb titer, and PASI90 response (based on NRI) will be created. All 3 endpoints will be plotted on the Y-axes by time (X-axis) for the full treatment period including SFU. Plots will be labeled and grouped into the 7 predefined ADAb categories (category 1, 2, 3, 4, 5, 6, and 9).

The following summaries of NAb data will be prepared by treatment group:

- Number and percentage of PASI90 responders at Week 16 and at Week 32, by NAb category (ADAb-negative, NAb-positive, ADAb-positive / NAb-negative). This will be repeated for IGA 0/1 responders. These data will also be presented graphically.
- Number and percentage of PASI90 responders over time (up to Week 16 and Week 32) separated by NAb category (ADAb-negative, NAb-positive, ADAb-positive/NAb negative). This will be repeated for IGA 0/1 responders (up to Week 16 and Week 32). These data will also be presented graphically.

4.6.1.4.2.4 Safety endpoints by ADAb and NAb summaries

Summaries include the number of TEAEs, number of study participants with TEAEs, percentage of study participants with TEAEs, EAIR with 95% CI, and EAER. TEAEs will be sorted by SOC, HLT and PT.

TEAEs by ADAb status and ADAb titer:

TEAEs of the study participants initially randomized to bimekizumab 320mg Q4W/Q8W treatment, or initially randomized to placebo and initiating bimekizumab 320mg Q4W treatment at Week 16, will be summarized by ADAb status based on all available data using the following categories:

- AEs starting before the first ADAb-positive result (study participants in Categories 2 and 5)
- AEs starting on or after the first ADAb-positive result (study participants in Categories 2, 3, 4, 5 and 6)
- AEs for study participants who are always ADAb-negative (study participants in Category 1)

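### The table of TEAEs by ADAb status lists Category 5 in a column to which it can contribute nothing, and omits Category 9 without saying so

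*SAP*

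**What the plan says.** SAP 4.6.1.4.2.4 summarizes the TEAEs of participants randomized to bimekizumab, or switched to it from placebo at Week 16, in three columns:

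- *before*: "AEs starting before the first ADAb-positive result (study participants in Categories 2 and 5"
- *on or after*: "AEs starting on or after the first ADAb-positive result (study participants in Categories 2, 3, 4, 5 and 6"
- *always negative*: "AEs for study participants who are always ADAb-negative (study participants in Category 1"

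Each participant's time at risk is divided at the first positive result. The table reports numbers of events, numbers and percentages of participants, and the exposure-adjusted incidence rate (EAIR) and event rate (EAER).

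The categories come from SAP 4.6.1.4.1.4. Category 5 "Includes study participants who are positive at Baseline and have at least one post-treatment sample (including SFU) that has titer value" at least 2.07 times the Baseline titer. Category 9 holds participants with a negative or missing Baseline sample and "more than one post-treatment samples that are missing/inconclusive, while other samples are ADA_b negative". It also holds those with a missing Baseline sample, one missing later sample and no positive result. Category 1 tolerates one missing or inconclusive post-Baseline sample when the Baseline sample is negative.

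Two general definitions matter. SAP 4.1.2 sets Baseline as "the latest measurement for that study participant up to and including the day of first IMP administration". SAP 4.5.2.1 sets the earliest TEAE: "TEAEs are defined as those AEs that have a start date on or following the first dose of IMP".

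**The concern.** Categories 3, 4, 5 and 6 are all ADAb-positive at Baseline. Three of them appear only under *on or after*; Category 5 appears under *before* as well, and the section gives no reason for the difference. A Baseline-positive participant has no period before the first positive result in which a TEAE could occur.

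The second gap is in coverage. The section says it summarizes the TEAEs of bimekizumab-treated participants, but participants in Category 9 have no column and no exclusion is stated. The individual plots specified in section 4.6.1.4.2.3 do include Category 9.

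This is the table a reader would use to judge whether adverse events go with antibodies. In a study of about 120 participants its cells will be small. A column whose percentage and rate describe different people, or a comparator that loses members for reasons linked to antibody status, makes that judgement harder.

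**Working it through.** The documents give no figure on this point to reproduce. Steps 1, 3 and 4 follow from the definitions; the counts in steps 2 and 5 and the withdrawal rate in step 4 are assumed.

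**1. Can Category 5 have a TEAE in the *before* column?** The Baseline sample is taken on or before Day 1, and a TEAE starts on Day 1 or later. For Category 5 the first positive result is the Baseline one. A TEAE before it would need a start day earlier than the sample day, and no permitted pair of days gives that. Events: 0. Time at risk before the first positive result: 0. Participants who switch from placebo do not change this, because SAP 4.1.4 shows only their post-switch data in the bimekizumab columns. Category 5 also receives by default any participant who is positive at Baseline and later but has no titers with which to classify the change.

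**2. Effect on the column.** Let x of n2 Category 2 participants have a TEAE before positivity, and let n5 be the size of Category 5.

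- Percentage without Category 5: x / n2. With it in the denominator: x / (n2 + n5).
- EAIR = 100 × (participants with the event) / (total time). EAER = 100 × (events) / (total time). Category 5 adds 0 to each numerator and 0 to the time, so both are unchanged.

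With n2 = 40 and x = 20 the percentage is 50.0%:

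| n5 | Percentage with Category 5 in N |
|---|---|
| 2 | 20/42 = 47.6% |
| 5 | 20/45 = 44.4% |
| 10 | 20/50 = 40.0% |

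**3. Coverage.** The mutually exclusive categories are 1 to 6 and 9 (7 and 8 are combinations). The three columns together list 1, 2, 3, 4, 5 and 6. Only Category 9 is left out.

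**4. Who falls in Category 9?** Protocol Table 1-1 places post-Baseline ADAb samples at Weeks 8, 16, 24 and 32/PEOT, and at SFU. SAP 4.1.3 assigns a PEOT sample to the next scheduled ADAb visit. For a Baseline-negative participant whose available samples are all negative, counting samples not taken after withdrawal as missing:

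| Stops | Missing at Weeks 8–32, PEOT sample taken | Category |
|---|---|---|
| By Week 8 | 3 (Weeks 16, 24, 32) | 9 |
| After Week 8, up to Week 16 | 2 (Weeks 24, 32) | 9 |
| After Week 16, up to Week 24 | 1 (Week 32) | 1; becomes 9 if PEOT is not done, or if SFU is counted and missed |
| After Week 24 | 0 | 1; becomes 9 only if PEOT and SFU are both missed and SFU is counted |

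A Baseline-negative participant who stops equally early but has one positive post-treatment sample is Category 2 and stays in the table. The documents give no withdrawal rate. Assuming 3% to 8% of the 90 randomized to bimekizumab stop before Week 16, 90 × 0.03 = 2.7 and 90 × 0.08 = 7.2. That is about 3 to 7 people at most, less those with a positive sample.

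**5. Direction of the Category 9 effect.** Suppose 36 of 60 always-negative participants (60.0%) have a TEAE when the early stoppers are included. Removing 5 stoppers of whom 2 had a TEAE gives 34/55 = 61.8%. Removing 5 of whom 4 had one gives 32/55 = 58.2%. The sign depends on the stoppers' own event frequency.

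**The case against.** **Intent.** Categories 2 and 5 together are Category 7, total treatment-emergent, and section 4.6.1.4.2.1 tabulates when participants first become treatment-emergent or boosted positive. If the split for Category 5 was meant to be its first boosted sample, listing it in both columns and Categories 3, 4 and 6 in one is coherent. This is plausible. But section 4.6.1.4.2.4 splits at the first positive result, and under the other reading the *before* column would hold time when the participant was already positive. The text needs correcting either way.

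**Denominator.** The section states no column N. SAP 4.1 bases safety percentages, unless otherwise specified, on participants with observed data for the variable. Someone with no time in the column might therefore be left out. This stands, so the dilution is conditional.

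**Category 9.** Declining to call a participant always negative when several samples are missing is reasonable. The group is counted in the nine-category table, its TEAEs appear in the overall tables on the Active Medication Set, and all AEs are listed. All of that stands. It does not excuse an unstated omission from this table.

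**A stronger reading.** A reader might infer that both features push toward an apparent excess of adverse events with antibodies. The documents do not support this. Step 5 shows that the Category 9 effect can go either way. An early stopper whose first positive sample is the PEOT or SFU sample also has the earlier AE that led to stopping counted under *before*, which would work against such an excess.

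**Conclusion.** The point holds, as a minor one. From the definitions alone, Category 5 contributes no TEAE and no time to the *before* column, and Category 9 has no column.

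The consequences are conditional. The percentages are diluted only if Category 5 is counted in the column N; percentage and rate in that column then rest on different populations. The sizes shown use assumed counts. Always-negative participants who stop by about Week 16 fall in Category 9 only if samples not taken after withdrawal count as missing. The SAP's definition of a missing sample makes no exception for these but does not address them. It would be too strong to say that all early ADAb-negative discontinuers are lost: those who stop after Week 16 and give PEOT and SFU samples remain in Category 1. Protocol 9.3.1 also expects few discontinuations before Week 16.

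Retention in the table can depend on antibody status, but the direction of any resulting bias is unknown. No hypothesis test or primary or key secondary conclusion is affected.

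**What to change.** In SAP 4.6.1.4.2.4:

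1. Restrict the *before* column to Category 2. If the first boosted sample was intended as the split for Category 5, state that split and relabel both columns. That option also needs a rule for participants placed in Category 5 because titers are unavailable, since no boosted sample can be dated for them.
2. Add a Category 9 (missing) column showing its N, TEAEs and time at risk. A footnote giving only N would disclose the omission but not the events.

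The definition of a missing sample should not be changed for the other ADAb outputs. Doing so would move participants among Categories 1, 6 and 9, and so alter the nine-category table and the individual plots.

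The cost is a wording change in one section and one extra column in one descriptive table. No additional data are needed.
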